The study will include thirty patients planned for major abdominal surgery in propofolremifentanil anesthesia combined with epidural analgesia. Internal carotid artery blood flow will be evaluated on the neck using duplex ultrasound. The study will be conducted one hour after the start of surgery and lasts for approximately half an hour. In the study, MAP is set pharmacologically at 80-85, 70-75 and 60-65 mmHg for a short time in random order. The level of 60-65 mmHg corresponds to the level at which MAP is maintained in clinical practice. Control of MAP is by intravenous infusion of noradrenaline, an  $\alpha$  - and  $\beta$  -adrenergic agonist.

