Development of a so-called mesenteric traction syndrome can affect MAP in the first hour of major abdominal surgery. Thus, the study is conducted from 60 min after incision and lasts for approximately half an hour. Anesthesia reduces MAP, but the reduction varies between patients and is affected by administration of propofol, remifentanil, and epidural anesthesia, fluid status, and surgical stimulation etc. The start of the study is postponed until any larger bleeding, transfusion or volume optimization is treated or finished. Before the start of the study, the infusion speed of propofol and remifentanil must have been constant for at least 10 min, and at least 15 min must have elapsed since the last bolus dose bupivacaine, as any changes in anesthesia may affect both cerebral and central hemodynamics. In case the infusion of propofol or remifentanil is changed or bolus bupivacaine is administered during the study, the experiment is halted, and the study is restarted when the anesthesia has been stable for 10 min. The experiment can only be restarted once and only data from the last trial with the highest number of evaluations are used.

In the experiment MAP is temporally set to 80-85, 70-75, and 60-65 mmHg by adjusting the infusion of noradrenaline. The order of evaluations is randomized by drawing an envelope just before the start of the experiment. Noradrenaline is short lasting and have no direct effect on CBF. The experiment lasts approximately 30 min until evaluations have been conducted at the three levels of MAP. If MAP does not drop to 60-65 mmHg by halting the infusion of noradrenaline this evaluation is not conducted but we expect that this will be the case in only few patients. In clinical practice noradrenaline is used to maintain MAP > 60 mmHg. The study is not an investigation of medicinal products as noradrenaline is used as a tool to control MAP.

Administration of noradrenaline is by a central venous or large peripheral catheter, using an electronic infusion pump, and infusion speed is adjusted slowly until the level of MAP is reached. Noradrenaline is effective within 1-2 min after administration and the effect lasts only for a few minutes. When MAP has been stable at the desired level for at least 3 min, measurements are conducted during the following 2 min. When the study is finished, control of MAP will be according to clinical practice. We consider that there is no increased risk by a short term increase in MAP to 80-85 mmHg.

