#### **Statistics**

Trial size: The minimal clinically important difference in internal carotid artery blood flow between evaluations at MAP 60-65 and 80-85 mmHg is considered to be 10% as evaluations using near-infrared spectroscopy indicate that intraoperative cerebral deoxygenation of > 10% associates to postoperative cognitive dysfunction.

A power calculation indicated that at least 18 patients were required to detect a difference in internal carotid artery blood flow of 10% corresponding to 19 ml/min assuming a standard deviation for the change of 27 ml/min (unpublished results from the study "Cerebral Blood Flow During Propofol Anaesthesia" NCT02951273) to obtain a 5% significance level and a power of 80%. We plan to include 30 patients.

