Statistical plan: The Effect of Blood Pressure on Cerebral Blood Flow During

Propofol Anesthesia

Brief Title: The Effect of Blood Pressure on Cerebral Blood Flow During Propofol Anesthesia

Official Title: The Effect of Blood Pressure on Cerebral Blood Flow During Propofol Anesthesia

Acronym: CA

Clinical trials ID: NCT03309917

Date: December 22 2017

Unique Protocol ID: H-17021598-61256

Statistical plan

Trial size: The minimal clinically important difference in internal carotid artery blood flow between

evaluations at MAP 60-65 and 80-85 mmHg is considered to be 10% as evaluations using near-

infrared spectroscopy indicate that intraoperative cerebral deoxygenation of > 10% associates to

postoperative cognitive dysfunction. A power calculation indicated that at a 5% significance level

and a power of 80% at least 18 patients are required to detect a difference in internal carotid artery

blood flow of 10% corresponding to 19 ml/min assuming a standard deviation for the change of 27

ml/min (unpublished results from the study "Cerebral Blood Flow During Propofol Anaesthesia" NCT02951273). We plan to include 30 patients.

The primary outcome is change in internal carotid artery flow when MAP is set to 60-65 and 80-85 mmHg. Secondary outcomes are 1) change in internal carotid artery flow when MAP is set to 60-65 and 70-75 mmHg, 2) change in internal carotid artery flow when MAP is set to 70-75 and 80-85 mmHg, and 3) the slope of linear regression of MAP and internal carotid artery flow for the evaluations when MAP was 60-65 and 70-75 mmHg as compared to that of the evaluations when MAP was 70-75 and 80-85 mmHg.

Values are averaged over 2 min. The internal carotid artery flow and conductance are corrected for changes in PaCO₂ from the value at the evaluation at MAP 60-65 mmHg using a CO₂ reactivity of 18%/kPa and for the S_cO₂ a correction factor of 4.3%/kPa is used (unpublished results from the study "Cerebral Blood Flow During Propofol Anaesthesia" NCT02951273). Analysis of the time points when MAP was set to 60-65, 70-75, and 80-85 mmHg is by a repeated measure mixed model, fit by restricted maximum likelihood in a structured covariance model with time as a fixed effect (Proc mixed; SAS 9.4, SAS Institute, Cary, NC, USA). Analysis of variables not normally distributed is after logarithmic transformation or by a Friedman test and if the test is significant changes are evaluated using Wilcoxon signed rank sum test.

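### MAP levels are given in randomised order, but the primary mixed model has no period term; adding one costs little and gains precision if patients share drift

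*SAP*

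**What the plan says.** The Protocol's Background states that "MAP is set pharmacologically at 80-85, 70-75 and 60-65 mmHg for a short time in random order", and Methods adds: "The order of evaluations is randomized by drawing an envelope just before the start of the experiment". Neither document says whether the envelopes are balanced over the six possible orders.

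For the primary analysis the SAP (Statistical plan) writes "Analysis of the time points when MAP was set to 60-65, 70-75, and 80-85 mmHg is by a repeated measure mixed model", and specifies that it is "fit by restricted maximum likelihood in a structured covariance model with time as a fixed effect". No period, order or sequence term appears there or in the slope model.

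Four other statements bear on the point:

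- Protocol, Methods limits drift before the start. For example, "the infusion speed of propofol and remifentanil must have been constant for at least 10 min". It also requires an interval since the last bupivacaine bolus and postpones the start for larger bleeding, transfusion or volume optimisation. Flow is corrected for PaCO2.
- An evaluation can be absent: "If MAP does not drop to 60-65 mmHg by halting the infusion of noradrenaline this evaluation is not conducted".
- A run can be repeated: "The experiment can only be restarted once and only data from the last trial with the highest number of evaluations are used".
- The sample size in Protocol, Statistics rests on "assuming a standard deviation for the change of 27 ml/min". The documents do not say whether that SD already contains drift over time.

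**The concern.** With randomised order, MAP level and period (first, second or third evaluation) are separate factors. The model names one factor and calls it 'time'. Because the SAP defines the time points by the MAP settings, the natural reading is that 'time' labels MAP level. If it meant chronological position instead, the model would contain no MAP-level effect and could not address the primary outcome.

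On the natural reading, a change in flow common to all patients from the first to the third evaluation is left in the residual. Randomising the order stops this from biasing the contrast, but the analysis does not use the known order to recover the lost precision. At stake are the width of the interval for the primary contrast and, if the orders are balanced, a test that runs below its nominal 5%.

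**Working it through.** **Inputs.** From the Protocol (Statistics) and the SAP: difference 19 ml/min (10%, so a reference flow of 19/0.10 = 190 ml/min), SD of the within-patient change 27 ml/min, significance level 5%, power 80%, at least 18 patients required, 30 planned. Shared drift is not given. It is **assumed** linear at 0, 3.8, 9.5 or 19 ml/min per period (0, 2, 5 or 10% of 190).

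**Step 1: the plan's own figure.** A two-sided paired t-test gives 77.8% power at n = 17 and 80.3% at n = 18, so the stated 18 is reproduced. At n = 30 power is 96.1%.

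**Step 2: closed form, orders drawn independently.** Over six equally likely orders, two given levels are one period apart in four and two periods apart in two. The position difference has mean 0 and variance (4/6)×1 + (2/6)×4 = 2. If drift *d* comes on top of the 27 ml/min, the SD of the paired change is √(27² + 2d²).

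| d (ml/min per period) | SD of change | Paired-t power, n = 30 |
|---|---|---|
| 0 | 27.0 | 96.1% |
| 3.8 | 27.5 | 95.5% |
| 9.5 | 30.2 | 91.5% |
| 19 | 38.1 | 75.2% |

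**Step 3: simulation of both models.** n = 30; independent within-patient errors with SD 27/√2; level means 0, 9.5 and 19 ml/min (all 0 for type I error). The fit is within-patient least squares, which equals REML with compound symmetry for complete data. MAP level alone leaves 58 error df; MAP level plus period leaves 56. Each cell has 20,000 trials.

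| d | Orders | Half-width without / with period | Power without | Type I error without |
|---|---|---|---|---|
| 0 | independent | 9.8 / 10.0 | 96.6% | about 5% |
| 3.8 | independent | 10.0 / 10.0 | 96.0% | about 5% |
| 9.5 | independent | 11.0 / 10.0 | 92.2% | about 5% |
| 19 | independent | 13.9 / 10.0 | 76.9% | about 5% |
| 0 | five per order | 9.8 / 9.8 | 96.6% | 4.9% |
| 3.8 | five per order | 10.0 / 9.8 | 96.3% | 4.4% |
| 9.5 | five per order | 11.0 / 9.8 | 94.4% | 2.9% |
| 19 | five per order | 14.0 / 9.8 | 83.9% | 0.5% |

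With the period term, power is about 96% (independent) or 96.6% (balanced) at every drift. Type I error over the independent-draw cells lies between 4.8 and 5.4% with or without the term; in the balanced cells it is 4.8-5.0% with it. With independent draws the term breaks even at about 3.8 ml/min per period.

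**Step 4: variations (10,000 trials per cell).**

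- *60-65 evaluation skipped in an assumed 10%, unrelated to order.* Half-width without the term is 10.3, 10.5, 11.5 and 14.5 against 10.5 with it (independent), and 10.2, 10.4, 11.5 and 14.6 against 10.3 (balanced).
- *SD of 27 already contains the drift, independent draws.* The error SD of the change is √(27² − 2d²) = 26.5, 23.4 and 2.6 for d = 3.8, 9.5 and 19. Half-width without the term stays at 9.8 and power at about 97%. With it the half-width is 9.8 at d = 3.8 and 8.7 at d = 9.5. A residual SD of 2.6 makes d = 19 hardly possible on this reading.
- *Patient-specific drift only (SD 9.5 ml/min per period).* No gain: power is 92.3% without and 91.2% with the term (independent), and 92.2% for both (balanced).

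**The case against.** The strongest reply is that the plan contains no error here. Randomising the order is itself the protection against time trends, and neither document promises a period term that the SAP then omits. The benefit depends wholly on a drift figure that the documents do not supply, and Protocol, Methods already acts on likely causes of drift. Start times are postponed patient by patient and one restart is allowed, so the first evaluation falls at different times after incision. What drift remains may be largely patient-specific, which the term does not remove. The one case in which power drops below 80% needs 19 ml/min per period with independent draws. That is a common shift of 2 × 19 = 38 ml/min from first to third evaluation, twice the difference the trial regards as clinically important. At half that drift, power without the term still exceeds 92%, because 30 patients are planned where 18 are required.

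All of this stands as a limit on size. The 19 ml/min row should be read as an extreme. The wording point is also modest, since the intended meaning of 'time' can be inferred. What the objection does not remove is the imbalance between cost and benefit. The order is already recorded by the design, the loss with no drift is about 2% of interval width at most, and the gain at 9.5 ml/min of shared drift on top of the SD of 27 is about 9 to 11%.

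**Conclusion.** The point holds as a cheap improvement. The primary model, as most naturally read, omits period although order is randomised within patients. With complete data the omission does not bias the 80-85 v 60-65 contrast over the randomisation, and it does not inflate type I error. Its cost is width, plus a conservative test if orders are balanced.

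The size is unknown because the documents give no drift. It is negligible up to about 4 ml/min per period, about 1 ml/min of half-width at 9.5, and large only at the extreme of the assumed range. These figures assume linear drift shared by all patients and compound symmetry; the SAP's structured covariance is not specified further. An unstructured covariance gives the same pattern with complete data. There is high confidence that no period term is named, but not that the gain will be material.

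**What to change.** In the SAP's Statistical plan, replace the single 'time' effect with two fixed effects: MAP level (three categories, the effect of interest) and period (first, second or third evaluation within the run whose data are used). Keep patient as the repeated unit, and state that the primary result is the 80-85 v 60-65 MAP-level contrast from this model. No change to the slope model or the sample size is proposed.

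The cost is a rewritten sentence and two of 58 error degrees of freedom. If there is no drift, the half-width goes from 9.8 to 10.0 ml/min with independently drawn orders and from 9.82 to 9.83 with balanced orders. The order is known from the drawn envelope, so nothing new has to be measured.

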## Hypotheses

- Internal carotid artery blood flow is higher when MAP is 80-85 mmHg as compared to a MAP of 60-65 mmHg.
- Internal carotid artery blood flow is higher when MAP is 70-75 mmHg as compared to a MAP of 60-65 mmHg.
- Internal carotid artery blood flow is higher when MAP is 80-85 mmHg as compared to a MAP of 70-75 mmHg.
- The slope of linear regression between changes in MAP and internal carotid artery blood flow is higher for the evaluations at a MAP of 70-75 and 60-65 mmHg than for the evaluations at a MAP of 80-85 and 70-75 mmHg.

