#### Methods

The study is a single-center, prospective cohort study of thirty consecutive patients planned for major abdominal surgery in propofol anesthesia. In case surgery is cancelled, or if gas anesthesia is used the patient will be excluded and excluded patients will be replaced. The number of dropouts is expected to be between zero to five patients. Patients will be recruited the day before surgery, at which time the internal carotid artery will be evaluated using ultrasound. In case the vessel cannot be visualized, e.g. due to high localization of the carotid bifurcation the patient will not be able to participate in the study.

Anesthesia and surgery are according to clinical practice. Anesthesia is induced by propofol and maintained by propofol and remifentanil. A thoracic epidural catheter is placed at Th8/9 or Th9/10 and epidural anesthesia is initiated before surgery by bupivacaine infusion 0.5%, 5 ml/hr. and bolus 15 mg bupivacaine that is repeated hourly. Stroke volume is optimized after induction of anesthesia by repeated administration of 250 ml 5% human albumin until the increase in stroke volume is less than 10%, and volume optimization is repeated in case of persistent decrease in stroke volume by more than 10%. Noradrenaline infusion (0.6  $\mu$  g/kg\*ml) is started after induction of anesthesia to maintain MAP > 60 mmHg and to avoid volume optimization when the circulation is dilated.

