## **Primary Outcome Measure:**

 Change in internal carotid artery blood flow when mean arterial pressure (MAP) is set to 80-85 and 60-65 mmHg

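### On the rank route of the SAP's fallback for non-normal variables, the single primary comparison (80-85 v 60-65 mmHg) is tested only after a significant three-level Friedman test: minor, and cheap to reword

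*SAP*

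**What the plan says.** The Protocol's Primary Outcome Measure section names a single pair of levels: "Change in internal carotid artery blood flow when mean arterial pressure (MAP) is set to 80-85 and 60-65 mmHg". The other two pairs and the comparison of slopes are secondary. The SAP agrees.

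For the main analysis the SAP states: "Analysis of the time points when MAP was set to 60-65, 70-75, and 80-85 mmHg is by a repeated measure mixed model". It attaches no overall test as a precondition to that model. It also does not name the 80-85 v 60-65 contrast from the model as the primary test.

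For variables that are not normally distributed, the SAP says that analysis "is after logarithmic transformation or by a Friedman test and if the test is significant changes are evaluated using Wilcoxon signed rank sum test". The preceding sentence lists the three MAP levels, so the natural reading is a Friedman test across all three. No variable is exempted. Nothing elsewhere overrides the rule, because the Protocol's Statistics section covers trial size only.

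That section says that "at least 18 patients were required to detect a difference in internal carotid artery blood flow of 10% corresponding to 19 ml/min" with an SD of the change of 27 ml/min, "to obtain a 5% significance level and a power of 80" percent. Thirty patients are planned.

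**The concern.** An overall test before pairwise tests is used to protect against picking one pair out of several. Here the primary pair was chosen in advance, so its own 5% test already has the intended error rate. Requiring a significant Friedman result as well can only remove significant results. It makes the primary test conservative, and the sample size calculation does not allow for that.

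The way into this route is also open. The SAP does not say what is checked for normality, or when the log is preferred to ranks. Flow can be skewed between patients while changes within patients are close to normal. A check on raw flow could then send near-normal changes down the rank route, which is where the precondition costs most. What is at stake is some power for the primary comparison and an analysis choice left open until the data are seen.

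**Working it through.** **1. The plan's own figure.** Inputs from the Protocol's Statistics section: difference 19 ml/min, SD of change 27 ml/min, alpha 5%, power 80%. Sidedness is not stated.

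- Normal approximation: n = ((1.960 + 0.842) × 27/19)² = 15.85, so 16.
- Two-sided paired t-test, noncentral t with noncentrality (19/27)√n: power is 77.8% at n = 17 and 80.3% at n = 18.

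So 18 is the smallest n that reaches 80% on a direct two-sided paired test of one pair. A one-sided test would need only 14. At n = 30 the direct t-test has 96.1% power. No Friedman step enters this calculation.

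**2. Effect of the precondition at n = 30.** Simulation with a true 80-85 v 60-65 difference of 19, independent errors scaled so that the SD of each pairwise change is 27, and complete data. The Friedman test uses chi-square on 2 df at 5%, and the Wilcoxon signed-rank test on the primary pair is at 5%. The rule as written counts a result only if both are significant. The documents do not give the 70-75 mean, so it runs from midway (least favourable) to the whole rise lying between 60-65 and 70-75. The Protocol's Hypotheses section expects the latter direction, since the slope "is higher for the evaluations at a MAP of 70-75 and 60-65 mmHg than for the evaluations" at the two upper levels.

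| Within-patient errors | Direct Wilcoxon | Friedman, then Wilcoxon |
|---|---|---|
| Normal | about 95% | 83-90% |
| t, 4 df | 97-98% | 93-96% |
| t, 3 df | 99% | 97-98% |
| Skewed (lognormal, sigma 0.8) | 99% | 99% |
| Normal, no difference at any level | about 5% | about 2% |

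The largest loss is 95 − 83 = 12 points, with normal errors and the midway mean. With non-normal errors it is about 0-5 points.

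**3. How often it would matter.** Assumptions not in the documents: lognormal flow between patients with CV 30% or 40%, baseline mean 190 ml/min (so that 19 is 10%), normal changes, n = 30, and a check that fails if Shapiro-Wilk gives p < 0.05 at any level.

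- A check on raw flow fails in 43-44% (CV 30%) or 60-61% (CV 40%) of trials.
- Raw and log flow both fail in 6-7% or 8-9%.
- A check on paired changes fails in about 5%.
- The precondition blocks an otherwise significant primary Wilcoxon result in 0.2-1.2% of all trials if the log is tried first, and in 2.2-7.4% if ranks are used whenever raw flow fails.

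**4. Price of removing it.** With no difference at any level, normal errors and n = 30, the chance of at least one significant pair among the three is about 4.4% as written. It is about 7.2% if the primary pair is tested directly and the Friedman step is kept for the other two. The primary pair's own rate is about 5%.

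**The case against.** The strongest reply is that this hardly matters. The default analysis is the mixed model, which carries no such precondition. The rank route needs a failed normality check and then a choice of ranks over the log, which the SAP names first. The larger loss arises with near-normal changes, where a check on residuals or paired changes would seldom lead to ranks. At 30 patients power stays above the 80% target in every case tried. All of this stands and sets the weight at minor.

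It is also fair that testing overall and then by pairs is a recognised approach, and that the Friedman step is the only multiplicity protection in the rank fallback. Removing it for the primary pair has the price shown in step 4, so the change is not free.

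A reader might infer that the primary analysis as a whole depends on a Friedman test, that the rule inflates false positives, or that the trial is underpowered. The documents support none of these. The rule applies only on the rank route, it is conservative, and 30 patients are planned against 18 required.

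A reader might also work with 25 patients, because "The number of dropouts is expected to be between zero to five patients". The same Methods section says that excluded patients are replaced, so that figure deserves little weight. Pairs may also be lost when 60-65 mmHg is not reached and "this evaluation is not conducted but we expect that this will be the case in only few patients". No number is given, and those pairs are lost with or without the Friedman step.

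**Conclusion.** The point holds as a minor one. On the rank route, and only there, the SAP makes the single primary comparison conditional on a three-level Friedman test that the comparison does not need and the sample size does not assume. The SAP also leaves open what is checked for normality and when ranks replace the log.

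The cost is at most about 12 points of power with near-normal changes and about 0-5 points where errors really are non-normal. These sizes depend on the planning values (19 and 27 ml/min), independent errors, complete data on 30 patients, and error shapes and a 70-75 mean that the documents do not give. How often the rule would bite is less certain still, because the between-patient distribution is assumed.

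**What to change.** In the SAP:

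1. State that the primary test is the 80-85 v 60-65 mmHg contrast from the mixed model.
2. State that normality is judged on model residuals or paired changes, not on raw flow, and that the log is tried before ranks.
3. Add that, if a rank test is still needed for the primary outcome, the Wilcoxon signed-rank test is run directly on all complete 80-85 v 60-65 pairs, whatever the Friedman result.
4. Keep the Friedman step for the two secondary pairs.

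Disclose that, with no true difference, this raises the chance of at least one significant pair from about 4.4% to about 7.2%. If control over all three pairs is wanted, also test the secondary pairs only when the primary is significant. In that setting no pair can then be significant unless the primary is, so the chance returns to about 5%.

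The cost is a few sentences of SAP wording. No patients or measurements are added, and the required 18 and planned 30 do not change.

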## Objective

The purpose of the study is to evaluate whether internal carotid artery blood flow is increased by maintaining MAP at a higher level than that used in clinical practice during propofol anesthesia. Further, we evaluate whether a lower limit of cerebral autoregulation can be detected by comparing the slopes of linear regression of internal carotid artery blood flow and MAP at the evaluations when MAP is 60-65 and 70-75 mmHg and when MAP is 70-75 and 80-85 mmHg.

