## **Secondary Outcome Measures:**

- 2. Change in internal carotid artery blood flow when MAP is set to 70-75 and 60-65 mmHg
- 3. Change in internal carotid artery blood flow when MAP is set to 80-85 and 70-75 mmHg
- Comparison of the slope of linear regression of MAP and internal carotid artery blood flow for the evaluations when MAP is set to 80-85 and 70-75 mmHg and that of the evaluations when MAP is set to 70-75 and 60-65 mmHg

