Difference in the slope of linear regression of changes in MAP and internal carotid artery flow for the evaluations at MAP 60-65 and 70-75 mmHg as compared to that for the evaluations when MAP was 70-75 and 80-85 mmHg is by a linear mixed model, fit by restricted maximum likelihood. The outcome parameter is relative change in internal carotid artery flow and the fixed effects are change in MAP, a condition factor for the two situations and an interaction factor to indicate a difference in slope. Values are presented as mean \pm SD or median with interquartile range

for not normally distributed data and statistical significance is set at P < 0.05. Figures are drawn in R for Windows (version 3.4.1) using the package ggplot2.

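### The planned slope comparison leaves its data layout undefined and, on the most direct reading, tests for a lower limit of autoregulation using only the scatter in step size

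*SAP*

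**What the plan says.** The Protocol (Objective) gives as its second purpose: "we evaluate whether a lower limit of cerebral autoregulation can be detected by comparing the slopes of linear regression". The fourth item under Hypotheses is directional: "The slope of linear regression between changes in MAP and internal carotid artery blood flow is higher for the evaluations" at the two lower MAP levels than at the two upper ones. The comparison is also a listed secondary outcome in both documents.

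The wording differs between places. The Protocol's Secondary Outcome Measures ("Comparison of the slope of linear regression of MAP and internal carotid artery blood flow") and the SAP's third secondary outcome ("the slope of linear regression of MAP and internal carotid artery flow for the evaluations when MAP was 60-65 and 70-75 mmHg") describe flow regressed on MAP level. The Hypotheses section and the SAP's model description speak of changes in MAP.

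The SAP says the comparison "is by a linear mixed model, fit by restricted maximum likelihood". It defines the response variable thus: "The outcome parameter is relative change in internal carotid artery flow". On the other side of the model equation, "the fixed effects are change in MAP, a condition factor for the two situations and an interaction factor to indicate a difference in slope". It names no random effect or residual covariance for this model; a structured covariance is mentioned only for the separate analysis of the three MAP levels. The only reference evaluation named is for the PaCO₂ correction ("from the value at the evaluation at MAP 60-65 mmHg"). Neither document gives a power for the slope comparison.

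**The concern.** The three omissions decide what is tested. If a patient supplies one pair of changes per step, the model has a separate intercept and slope for each step, and almost all MAP changes lie close to 10 mmHg. A 10% rise in flow over the lower step is then fitted almost equally well by an intercept of 10% with slope 0 as by an intercept of 0 with slope 1 %/mmHg. Only the departures of the steps from 10 mmHg tell these apart.

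If instead both ends of each step are entered, the full 10 mmHg is used. The 70-75 evaluation then belongs to both steps, and that dependence has to be modelled.

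Two analysts could follow the SAP faithfully and reach different conclusions from the same data. A non-significant interaction could also be misread as evidence that no lower limit exists in this MAP range.

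**Working it through.** **The plan's own figure.** Two-sided paired t-test, difference 19 ml/min, SD 27 ml/min, alpha 5%: n = 18 gives 80.3% power, so the stated 18 reproduces. Thirty patients give 96%. This concerns the primary contrast only.

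**Inputs.** Three MAP bands, each 5 mmHg wide with centres 10 mmHg apart (Protocol, Methods); n = 30; SD of change 27/190 = 14.2%, where 190 ml/min follows from 19 ml/min being 10%. Assumptions not in the documents: MAP uniform within each band; the 14.2%, stated for the 20 mmHg contrast, applied to a step; target effect 1 %/mmHg in the lower step and 0 in the upper.

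**Step 1: scatter in step size.** Variance within a band is 25/12 = 2.08. Variance of a step is 2 × 2.08 = 4.17 (SD 2.04 mmHg). Mean squared step is 100 + 4.17 = 104.2, and 4.17/104.2 = 4.0%. With every MAP at a band edge, the most extreme case if levels vary independently, the share is 12.5/112.5 = 11%.

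**Step 2: one change per step.** The SE of one step's slope is about 14.2/(2.04 × √30) = 1.27 %/mmHg. Through the shared 70-75 evaluation, the MAP changes correlate -0.5 and so do the errors, so the two slopes correlate about +0.25. The SE of their difference is 1.27 × √(2 × 0.75) = 1.56. An effect of 1 %/mmHg is therefore about 0.6 SE. Simulation gives SEs of 1.5-1.7 and power of about 5-11%.

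**Step 3: per-patient slopes.** Let s² be the error variance of one evaluation. If all the variance is error, s² = 14.2²/2 = 100.8. With 10 mmHg steps the slope difference is (2·F70 − F60 − F80)/10, with variance 6s²/100 = 6.05 and SD 2.46. The SE is 2.46/√30 = 0.45, about 3.5 times smaller than in step 2. A patient slope common to both steps cancels from this difference, so if 75% of the variance is of that kind, s² falls to 25.2 and the SE to 0.22. Simulated power is about 52%, 65%, 80% and 98% at shares of 0, 25, 50 and 75%, with type I error of 4-5%.

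**Step 4: sensitivity to the SD.** These figures take errors as independent by level. At SD 10%, power is 4-18% with one change per step and 73-88% with valid full-step analyses. At SD 5% it is 8-51% against over 99%. With edge scatter and SD 5%, one change per step reaches 93%.

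**Step 5: both ends of each step as rows.** Treated as independent, the four rows imply variance 4s²/100 for the slope difference; the true value is 6s²/100. The nominal cut-off of 1.96 becomes 1.96/√1.5 = 1.60, a two-sided error of about 11%. Simulation with ordinary errors gave 11% with no variation in patient slopes and 2% when 75% of the variance was a common slope. With a patient random intercept it gave 12-18% and 3-8% respectively. The overall range is about 2-18%.

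**Step 6: reference flow in a full-step analysis.** If flow were exactly proportional to MAP and each step were expressed relative to its own lower-level flow, the slopes would be 100/62.5 = 1.60 and 100/72.5 = 1.38 %/mmHg. That is a spurious difference of 0.22 in the hypothesised direction. With one reference per patient it is zero.

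**The case against.** The strongest reply is that the SAP is incomplete here and not shown to be wrong: a sensible analyst could choose a layout and covariance that work. That is fair for the full-step reading. A reader might infer that the planned model inflates the false-positive rate. The documents do not support this. They specify no random intercept, and the error under such a model runs from conservative to inflated depending on how much patients' slopes vary, which is unknown. Nor do they say that each step uses its own lower flow as denominator, so the 0.22 %/mmHg is conditional too.

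A reader might also infer that the slope test has negligible power whatever the data. That goes too far. The documents give no SD for a 10 mmHg step, and with a small SD and wide scatter the one-change-per-step model can have good power. Low power and a wrong error rate are moreover alternatives under different readings and do not add up.

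The loss of information relative to a full-step analysis stands. It follows from the design of the bands and appears at all three SDs examined. The text also leans towards the weaker layout: the SAP's outcome is a change, its covariate is a change in MAP, and it includes a condition factor.

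The PaCO₂ reference for patients who lack a 60-65 evaluation is a separate matter and is not part of this point.

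**Conclusion.** The concern holds and should be fixed. The SAP does not define the rows, reference flow or within-patient covariance for the slope comparison. On its most direct reading the test discards nearly all the information in the 10 mmHg steps: power is about 5-11%, against 52-98% for per-patient slopes. These figures assume 1 versus 0 %/mmHg, 30 patients, MAP uniform within bands and a borrowed SD of 14.2%; the range for per-patient slopes reflects how much of the variance is a patient slope common to both steps. The relative loss is secure; the absolute level is not.

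On the alternative reading, nominal type I error is not guaranteed unless the dependence through the 70-75 evaluation is modelled.

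This is a secondary outcome for which no power is claimed, though it carries the study's second stated purpose. The primary outcome, the two other flow comparisons and the minimum of 18 patients are unaffected.

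**What to change.** Replace the slope model in the SAP by a per-patient analysis:

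- For each patient, compute a lower-step slope (60-65 to 70-75) and an upper-step slope (70-75 to 80-85), each as flow change divided by achieved MAP change.
- Express flow as a percentage of one reference per patient for both steps, for example the mean of that patient's three evaluations.
- Test the within-patient difference of the two slopes by a paired t-test and report it with a 95% CI.
- State that a non-significant difference is not evidence that no lower limit exists. No power figure needs to be stated.

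The cost is SAP wording only; the data and measurements are the same. The downside is that patients without a 60-65 evaluation do not contribute. The Protocol expects few of these, and their number should be reported. If, as an assumption, 5 of 30 were missing, the SE would rise by a factor of √(30/25) = 1.10.
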